5.9.3. Sensitivity Analyses

5.9.3.1. Treatment Effect at Final Dose Levels

To assess the treatment effect at the final dose level, a sensitivity analysis will be conducted on the mITT set using the MMRM analysis method described in [Section 5.9.2](#) with treatment defined as the actual final dose level achieved. The final dose level is defined as the dose received at the Week 26 timepoint or at the time of early termination if the subject achieved a minimum of 5 mg prior to discontinuation.

5.9.3.2. Treatment Effect based on Actual Treatment Received

Should a discrepancy between the study treatment received and the randomized treatment assignment occurred in 6 or more subjects, a sensitivity analysis may be conducted based on the study treatments that subjects actually received using the MMRM analysis method described in [Section 5.9.2](#).

5.9.3.3. Remote Assessments Excluded (treated as missing)

In addition, a sensitivity analysis excluding the MDS-UPDRS Part II + Part III combined score obtained remotely may be performed if such remote assessments are conducted due to COVID-19 restrictions. It should be noted that the study only has provision of remote assessments for Parts I & II of the MDS-UPDRS assessments, as the clinician administered motor examination required for Part III cannot be reliably completed remotely.

5.9.3.4. Impact of Missing Values Handling

Whilst every effort will be made to prevent avoidable missing values during the study conduct ([National Research Council, 2010](#)), it is unrealistic to expect no missing values in clinical trials. The impact of missing values on the analysis results will be assessed by the sensitivity analyses described below.

Under Missing at Random (MAR) Assumption

Multiple imputation (MI) will be performed to replace each missing value with a set of plausible values that represent the uncertainty about the correct value to impute. The Markov chain (MCMC) method will be utilized for the mITT set. SAS PROC MI will be used to generate 27 possible imputed datasets: Each of these datasets will be analyzed using PROC MIXED in SAS using the MMRM model as described in [Section 5.9.2](#). The results of the analyses of the datasets will be combined using PROC MIANALYZE to produce an inferential result.

Considerations of Data Potentially Missing Not at Random (MNAR)

A pattern mixture model (PMM) approach will be used to address potentially MNAR patterns. The following three patterns of subjects in the mITT set will be considered:

- 1) Subjects with no missing values from discontinuation or from initiation of prohibited Parkinson's disease concomitant mediation during treatment period.
- 2) Subjects with missing values from the types of ICEs below will be considered having MNAR
 - a. Subjects who discontinue due to reasons, as recorded on the eCRF, of lack of efficacy, adverse events associated with motor symptoms of Parkinson's disease, physician decision, and withdrawal by subject.
 - b. Subjects who initiated concomitant Parkinson's disease medications (ATC classifications of ADAMANTANE DERIVATIVES, DOPAMINE AGONISTS, MONOAMINE OXIDASE B INHIBITORS, OTHER ANTI-PARKINSON DRUGS, OTHER DOPAMINERGIC AGENTS, or DOPA AND DOPA DERIVATIVES) after the first dose of IMP and prior to the last dose of IMP with a use duration of 7 days or more will be considered having a potential confounding ICE. The efficacy data post ICE will be treated as missing with the missing pattern of MNAR.

The MNAR cases will be identified and documented prior to database lock and unblinding ([Section 9.5](#)).

- 3) Subjects with missing values from the type of ICEs below will be considered as having MAR
 - a. Missing values after discontinuation due to reasons, as recorded on the eCRF, of death, pregnancy, loss to follow-up, adverse event unrelated to motor symptoms of Parkinson's disease, non-compliance, site termination, protocol deviation, failure to meet continuation criteria and other will be considered as MAR.

The MNAR pattern 2) above in the active treatment group will be imputed using the jump to reference (J2R) method (Cro et. al. 2020) by assuming that patients jump to behave like those in the placebo group following their last observed time point. However, such MNAR in the placebo group will still be imputed as MAR using the standard multiple imputation method.

The MAR patterns 3) will be imputed using the standard multiple imputation method described above.

Other missing values due to missed visits/assessments before endpoint or discontinuation will also be assumed as MAR and imputed using the standard multiple imputation method for all three patterns.

Core codes for MAR and MNAR imputations are provided in [Section 9.6](#).

Under Missing Completely at Random (MCAR) Assumption

An additional sensitivity analysis will be conducted on the Endpoint (Week 26) Completer set using the MMRM analysis method described in [Section 5.9.2](#).

5.9.4. Subgroup Analyses

Subgroup analyses of the primary endpoint will be made based on the mITT set to assess consistency of the intervention effect across the following subgroups:

- Age group: < 65 vs \geq 65 years
- Sex: female vs male
- Hoehn and Yahr Status at screening: 1 vs 1.5 vs 2
- Baseline MDS-UPDRS Part II score: \leq baseline median vs $>$ baseline median (median of the mITT set regardless of treatment group)
- Baseline MDS-UPDRS Part III score: \leq baseline median vs $>$ baseline median (median of the mITT set regardless of treatment group)
- Use of concomitant MAO-B inhibitor: yes vs no
- Years since initial diagnosis: (<1 year vs 1 to < 2 years vs 2 to < 3 years)
- Race: white vs other
- Region: United States vs Non-US

If the number of subjects within a subgroup is too small (less than 10% of the mITT set), the subgroup categories may be redefined prior to unblinding the study or the specific subgroup analysis may not be performed. Provided that the sample sizes in the subgroups allow, the MMRM analysis method described in [Section 5.9.2](#) will be applied to the subgroup analysis (excluding the covariate of MAO-B inhibitor use in the MAO-B subgroup models). The treatment effect across subgroups will be summarized by forest plots.

5.10. Key Secondary Efficacy Analyses

5.10.1. Secondary Estimand 1

The key research question for the first secondary efficacy variable will be addressed with an estimand based on the following attributes:

- 1) Treatments: treatments as randomized regardless of the actual treatment received or the final dose level achieved following the titration steps.
- 2) Target study population of interest: subjects in the modified intent-to-treat (mITT) population regardless the completion status of dose titration steps.
- 3) Endpoint (variable) of interest: change from baseline to Week 26 in the MDS-UPDRS Part II Score.
- 4) Population level summary of interest: estimated mean difference between each tavapadon (CVL-751) dose group and placebo group in the endpoint of interest.
- 5) Strategy for Intercurrent events (ICEs): a hypothetical strategy will be used to address intercurrent events (ICEs) of potential death, treatment discontinuations, missed visits/assessments, and start of prohibited concomitant Parkinson's disease medications (see definitions in [Section 5.9.1](#)). The data after treatment discontinuations or after the start of prohibited concomitant Parkinson's disease treatments will be censored under the hypothetical strategy.

5.10.1.1. Main Analytical Approach

Similar to the analysis of the primary efficacy variable, the change from baseline to each study visit in MDS-UPDRS Part II score will be summarized by visit and treatment group. A mixed model repeated measures (MMRM) analysis will be used with fixed effect of treatment group, visits, and interaction between treatment group and visit, and MAO-B inhibitor use. The baseline value of MDS-UPDRS Part II score will be included as a covariate. Subject will be included as a random effect. An unstructured covariance structure will be used for the repeated measures. If the unstructured covariance matrix results in convergence issue, the heterogeneous Toeplitz covariance structure followed by the heterogeneous first-order autoregressive (AR(1)) structure will be used. The Kenward-Roger approximation will be used to estimate the denominator degrees of freedom. The difference between each active dose and placebo at the endpoint visit (Week 26) will be estimated based on the Least Squares Mean (LSMean) difference derived from the MMRM with the associated 95% confidence intervals (CI) and P-values. A Cohen's D value will also be derived as the ratio of the estimated difference to the population standard deviation at each visit estimated from the model (the square root of the diagonal elements of the estimated covariance matrix). The missing values, including missing due to missed visits or early termination due to COVID-19 control measures, are assumed to be missing at random (MAR) in the main MMRM analysis. Sensitivity analyses will be performed to assess the impact of deviation from MAR assumptions on the analysis results. Time curve plots will be presented for both raw Mean (SEM) and LSMean (SE).

5.10.1.2. Sensitivity Analyses

The sensitivity analyses described in [Section 5.9.3](#) for the primary estimand will also be performed for the secondary efficacy estimand 1.

5.10.1.3. Subgroup Analyses

The subgroup analyses described in [Section 5.9.4](#) for the primary estimand will also be performed for the secondary efficacy estimand 1.

5.10.2. Secondary Estimand 2

The key research question for the second secondary efficacy variable will be addressed with an estimand based on the following attributes:

- 1) Treatments: treatments as randomized regardless of the actual treatment received or the final dose level achieved following the titration steps.
- 2) Target study population of interest: subjects in the modified intent-to-treat (mITT) population regardless the completion status of dose titration steps.
- 3) Endpoint (variable) of interest: proportion of responders, defined as subjects with a score of “much improved” or “very much improved” on the PGIC, at Week 26.
- 4) Population level summary of interest: : estimated difference expressed as odds ratio between each tavapadon (CVL-751) dose group and placebo group in achieving response.
- 5) Strategy for Intercurrent events (ICEs): a hypothetical strategy will be used to address intercurrent events (ICEs) of potential death, treatment discontinuations, missed visits/assessments, and start of prohibited concomitant Parkinson’s disease medications (see definitions in [Section 5.9.1](#)). The data after treatment discontinuations or after the start of prohibited concomitant Parkinson’s disease treatments will be censored under the hypothetical strategy.

5.10.2.1. Main Analytical Approach

The number and percentage of responders will be summarized by visit and treatment group. The binomial repeated measures up to Week 27 will be analyzed using a generalized linear mixed model with logit link (SAS® GLIMMIX procedure). The treatment group, MAO-B inhibitor use, visits, and interaction between treatment group and visit will be included as fixed effect. An unstructured covariance structure will be used for the repeated measures. If the model does not converge with the unstructured covariance structure, the heterogeneous Toeplitz structure will be used. The odds ratio of each active dose to placebo at the endpoint visit will be estimated based on the Least Squares Mean difference in logit between the treatment groups from the GLIMMIX model with the associated 95% confidence intervals (CI) and P-values. The missing values are assumed to be missing at random, including missing due to missed visits or early termination due to COVID-19 control measures. Sensitivity analyses will be performed to assess the impact of deviation from MAR assumptions on the analysis results.

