9.4.1 Efficacy Analyses

The efficacy endpoints will be assessed for each of the 2 dose levels of tavapadon versus placebo. A hierarchical testing procedure is planned for the primary and key secondary endpoints, in the following order, to control the Type I error rate at the 0.05 level (2-sided).

1. Tavapadon 15 mg QD versus placebo on the primary endpoint

2. Tavapadon 5 mg QD versus placebo on the primary endpoint
3. Tavapadon 15 mg QD versus placebo on the key secondary endpoint of MDS-UPDRS Part II score change from baseline
4. Tavapadon 15 mg QD versus placebo on the key secondary endpoint of percentage of responders on the PGIC score
5. Tavapadon 5 mg QD versus placebo on the key secondary endpoint of MDS-UPDRS Part II score change from baseline
6. Tavapadon 5 mg QD versus placebo on the key secondary endpoint of percentage of responders on the PGIC score

The analysis methods for the primary and secondary endpoints are summarized in [Table 9](#). Additional details will be provided in the statistical analysis plan.

Table 9 Efficacy Analysis

Endpoint	Statistical Analysis Methods
Primary	
The primary efficacy endpoint (the change from baseline to endpoint in the MDS-UPDRS Parts II and III combined score) will be analyzed using an MMRM. The change from baseline at each postbaseline timepoint will be included in the MMRM as repeated measures. The baseline score will be included as a covariate, and treatment group, visit, the interaction between treatment group and visit, and the stratification factor (concurrent use of MAO-B inhibitor; yes/no) will be included as fixed factors. An unstructured covariance structure will be utilized. The difference between each tavapadon dose level and placebo at endpoint will be estimated based on the LSMeans from the MMRM. A hypothetical strategy will be used to address ICEs of potential death, treatment discontinuations, missed visits/assessments, and start of prohibited concomitant medications. The data after treatment discontinuations or after the start of prohibited concomitant medications will be censored under the hypothetical strategy. The missing values are assumed to be MAR in the primary analysis, including missing due to COVID-19 control measures. Sensitivity analyses will be performed to assess the impact of deviation from MAR assumptions on the analysis results.

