Key Secondary	
The key secondary endpoint of the change from baseline to endpoint in the MDS-UPDRS Part II score will be analyzed using an MMRM analysis similar to the analysis of the primary endpoint. Similar sensitivity analyses will also be performed.
 
The key secondary endpoint of percentage of responders at endpoint, defined as a score of “much improved” or “very much improved” on the PGIC, will be analyzed using the SAS® GLIMMIX procedure for binomial data with logit link. This generalized linear mixed model analysis will include response data from each postbaseline visit as repeated measures with treatment group, visit, and interaction between treatment group and visit as fixed effects. An unstructured covariance structure will be used for the repeated measures. If the model fails to converge with the unstructured covariance structure, the heterogeneous Toeplitz structure or further reduced covariance structure may be used.

Table 9 Efficacy Analysis

Endpoint	Statistical Analysis Methods
Secondary	Continuous secondary endpoints (CGI-S, CGI-I, PDQ-39, Schwab and England ADL Scale, and EQ-5D-5L index and VAS scores) will be analyzed in a manner similar to that used for the primary efficacy endpoints. Categorical endpoints (proportion of subjects who improved based on the CGI-S or CGI-I) will be analyzed in a manner similar to that used for the key secondary endpoint of the percentage of responders on the PGIC at endpoint.

Abbreviations: ADL = activities of daily living, CGI-I = Clinical Global Impression – Improvement, CGI-S = Clinical Global Impression – Severity of Illness, EQ-5D-5L = EuroQol 5 Dimension 5 Level, ICE = intercurrent event, LSMean = least square mean, MAO-B = monoamine oxidase B, MAR = missing at random, MDS-UPDRS = Movement Disorder Society – Unified Parkinson’s Disease Rating Scale, MMRM = Mixed Model for Repeated Measures, PDQ-39 = 39-Item Parkinson’s Disease Questionnaire, PGIC = Patient Global Impression of Change, VAS = visual analog scale.

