3.1.2. Patient Global Impression of Change (PGIC)

The PGIC is the patient-reported outcome in a 7 point scale to rate how much the patient's illness has improved or worsened relative to the baseline state at the beginning of the intervention. The qualitative assessment of meaningful change is determined by the patient in response to the question, "Compared to your condition at the beginning of treatment, how much has your condition changed?" Scores are: 1=very much improved; 2=much improved; 3=minimally improved; 4=no change; 5=minimally worse; 6=much worse; and 7=very much worse.

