5.2. Populations for Analyses

The analysis populations are defined [Table 4](#).

Table 4: Populations for Analysis

Population	Description	Analysis
ITT	All randomized subjects	Demographic and Baseline Characteristics
FAS	All randomized subjects who receive at least 1 dose of IMP. This will be the safety analysis set.	Safety analysis
mITT	All randomized subjects who receive at least 1 dose of IMP and have a baseline and at least one postbaseline MDS-UPDRS assessment.	Primary analysis set for efficacy
Endpoint completers	All subjects in the mITT population who have an MDS-UPDRS assessment at baseline and endpoint	Sensitivity analysis set for efficacy
PK	All randomized subjects who receive at least 1 dose of tavapadon and have at least one measurable scheduled tavapadon (CVL751) concentration	PK analysis set

Abbreviations: FAS = full analysis set, IMP = investigational medicinal product, ITT = intent-to-treat, mITT = modified intent-to-treat, PK = pharmacokinetic, MDS-UPDRS = Movement Disorder Society – Unified Parkinson’s Disease Rating Scale.

[figure not shown]

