5.5. Strata and Covariates

The randomization is stratified by concurrent use of MAO-B inhibitor. This factor is planned to be included as a covariate in the efficacy analyses. However, due to isolated administrative errors at a few sites during randomization through IRT system, 15 subjects were randomized to the incorrect strata (3 non-MAO-B inhibitor users were randomized to the MAO-B inhibitor use stratum and 12 MAO-B inhibitor users were randomized to the non-user stratum; details in [Section 9.7](#)). The actual MAO-B inhibitor use status, as recorded in eCRF, will be used as a covariate instead of the randomization strata in these cases.

The baseline value of each efficacy variable (if applicable) will also be included as a covariate in the efficacy analyses.

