5.9.2. Main Analytical Approach

The change from baseline to each study visit in MDS-UPDRS Part II and III combined score will be summarized by visit and treatment group. A mixed model repeated measures (MMRM) analysis will be used to analyze the data from all post-randomization timepoints up to Week 27 with fixed effect of treatment group, visits, interaction between treatment group and visit, and baseline MAO-B inhibitor use. The baseline value of MDS-UPDRS Part II and III combined score will also be included as a covariate. Subject will be included as a random effect. An unstructured covariance structure will be used for the repeated measures. If the unstructured covariance matrix results in convergence issue, the heterogeneous Toeplitz covariance structure followed by the heterogeneous first-order autoregressive (AR(1)) structure will be used. The Kenward-Roger approximation will be used to estimate the denominator degrees of freedom. The difference between each active dose and placebo at the endpoint visit (Week 26) will be estimated based on the Least Squares Mean (LSMean) difference derived from the MMRM with the associated 95% confidence intervals (CI) and P-values. A Cohen's D value will also be derived as the ratio of the estimated difference to the population standard deviation at each visit estimated from the model (the square root of the diagonal elements of the estimated covariance matrix). The missing values, including missing due to missed visits or early termination due to COVID-19 control measures, are assumed to be missing at random (MAR) in the main MMRM analysis. Sensitivity analyses will be performed to assess the impact of deviation from MAR assumptions on the analysis results. Time curve plots will be presented for both raw Mean (SEM) and LSMean (SE).

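### The PGIC responder model has no baseline severity covariate; prespecifying one is a cheap change that could add a little power at H4 and H6 if baseline severity is prognostic

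*SAP*

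**What the plan says.** SAP 5.10.2.1 models PGIC response at all visits up to Week 27 with a logit link. Its terms are: "The treatment group, MAO-B inhibitor use, visits, and interaction between treatment group and visit will be included as fixed effect". Protocol 9.4.1 (Table 9) has no severity term either; it describes "repeated measures with treatment group, visit, and interaction between treatment group and visit as fixed effects".

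The general rule is in SAP 5.5: "The baseline value of each efficacy variable (if applicable) will also be included as a covariate in the efficacy analyses". The PGIC is first collected after baseline and asks how far the illness has "improved or worsened relative to the baseline state at the beginning of the intervention", so it has no baseline value for that rule to bring in.

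The other two endpoints in the hierarchy are treated differently. For the primary endpoint, SAP 5.9.2 states: "The baseline value of MDS-UPDRS Part II and III combined score will also be included as a covariate". Section 5.10.1.1 does the same for Part II with the baseline Part II score.

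A severity measure is at hand. The mITT set (SAP 5.2, Table 4) requires subjects to "have a baseline and at least one postbaseline MDS-UPDRS assessment", and inclusion criterion 8 requires Part II and Part III scores at the Baseline Visit.

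PGIC response is a confirmatory endpoint. Step 4 of the sequence in Protocol 9.4.1 is "Tavapadon 15 mg QD versus placebo on the key secondary endpoint of percentage of responders on the PGIC score"; step 6 is the same comparison for 5 mg. SAP 5.3 labels these H4 and H6.

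**The concern.** In a logistic model, adjusting for a baseline variable that predicts the outcome makes the test of treatment more powerful. Here the plan uses that gain for the two MDS-UPDRS endpoints but not for the PGIC responder endpoint, apparently because the covariate rule is tied to each variable's own baseline.

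The reach is slightly wider than the two PGIC tests. Under the fixed sequence in SAP 5.4, failing H4 stops testing, so H5 (Part II, 5 mg) and H6 are lost with it. Power at H4 therefore affects three of the six steps, provided H1 to H3 have succeeded.

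**Working it through.** **Starting point.** Neither document gives a power or a responder rate for the PGIC, so there is no PGIC figure to reproduce. The number of evaluable subjects comes from the primary sample size: 174 per group and 27% dropout (SAP 1.2, Protocol 9.2).

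- Formula: n per group = 2(z₁₋α/₂ + z₀.₉₀)² × SD² / Δ², with SD 9 and Δ 4.
- SAP, two-sided α 0.025: 2 × (2.241 + 1.282)² × 81/16 = 125.7, so 126; 126 / 0.73 = 172.6, so 173 against the stated 174. This reproduces within rounding.
- Protocol, two-sided α 0.05: 107 evaluable and 147 randomized. With 174 randomized the power is 94.3%, consistent with the protocol's claim of at least 90%.
- Evaluable per arm: 174 × 0.73 = 127.

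The documents differ on the α used for sample size. That does not matter here, because the hierarchy tests each step at two-sided 0.05.

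**Power without the covariate (one visit, assumed 25% versus 40% responders).**

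- Log odds ratio: ln(0.40/0.60) − ln(0.25/0.75) = 0.693, an odds ratio of 2.00.
- SE: √[1/(127 × 0.25 × 0.75) + 1/(127 × 0.40 × 0.60)] = 0.2735.
- Power: Φ(0.693/0.2735 − 1.96) = Φ(0.574) = 71.7%.

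**Power with the covariate.** Baseline severity is taken as a standard normal variable with a given odds ratio per SD. The intercept and treatment coefficient are solved so that the overall responder rates stay at 25% and 40%. The SE comes from the expected information matrix for intercept, treatment and covariate. For an odds ratio of 2.0 per SD, the treatment coefficient becomes 0.7605 (odds ratio 2.14) and its SE 0.2876. Power is then Φ(0.7605/0.2876 − 1.96) = Φ(0.684) = 75.3%. Both coefficient and SE grow, but the coefficient grows more.

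Power (%) by assumed responder rates and assumed odds ratio per SD of baseline severity; OR 1.0 equals the unadjusted power:

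| Placebo vs active | OR 1.0 | OR 1.2 | OR 1.5 | OR 2.0 | OR 3.0 |
|---|---|---|---|---|---|
| 20% vs 35% | 75.5 | 75.7 | 76.7 | 78.7 | 82.3 |
| 25% vs 40% | 71.7 | 72.0 | 73.1 | 75.3 | 79.3 |
| 30% vs 45% | 69.0 | 69.3 | 70.5 | 72.9 | 77.2 |
| 40% vs 55% | 66.4 | 66.8 | 68.0 | 70.5 | 75.1 |

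The gain is 0 at OR 1.0, 0.2 to 0.4 points at 1.2, 1.2 to 1.6 at 1.5, 3.2 to 4.1 at 2.0 and 6.8 to 8.7 at 3.0.

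**Simulation check** (4,000 trials per setting, 25% versus 40%). OR 1.0: 72.0% unadjusted, 71.9% adjusted. OR 1.5: 72.2% to 74.0%. OR 2.0: 72.2% to 75.3%. These agree with the formula, and there is no visible loss when the covariate is not prognostic.

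**Change in the odds ratio.** With a marginal odds ratio of 2.00, the conditional one is 2.05 at a covariate OR of 1.5 and 2.14 at 2.0.

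**The case against.** The strongest objection is that no loss has been shown. The gain exists only if baseline MDS-UPDRS predicts PGIC response, and nothing in the documents says that it does. The PGIC is itself rated against each subject's baseline state, and eligibility narrows the range of severity (modified Hoehn and Yahr 1 to 2, diagnosis under 3 years). The association could be weak. This stands, and it is why the point is conditional.

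Four stronger readings are tempting and are not supported:

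- A reader might infer that the plan contradicts its own covariate rule. It does not: SAP 5.5 limits the rule to cases where it applies.
- A reader might infer that the covariate is guaranteed for every mITT subject. The set requires a baseline assessment, not a valid combined score. SAP 3.1.1.4 sets a part score to missing when too many items are absent, and 3.1.1.5 needs both parts on the same date. With inclusion criterion 8 such cases should be rare, but they are possible.
- A reader might infer that the covariate would repair the missing-at-random assumption. The documents do not show that dropout depends on baseline severity, and earlier PGIC responses already enter the model. No such benefit has been calculated. SAP 5.10.2.2 does omit the multiple-imputation check for this endpoint, but it imputes potential MNAR cases as non-responders.
- A reader might infer that changing the odds ratio is harmless because the model already conditions on MAO-B inhibitor use. That is the randomization stratification factor, so adjusting for it follows from the design. A further conditioning variable needs its own words in the estimand.

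**Conclusion.** The point holds as an optional, low-cost improvement. The model omits baseline severity for a confirmatory endpoint when a suitable measure is already collected. Prespecifying it could raise power by about 0 to 2 points for a weak predictor (odds ratio per SD up to 1.5) and 3 to 4 points for a moderate one (2.0). It would add nothing if baseline severity is not prognostic. The comparison is unbiased and its Type I error controlled either way.

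These figures rest on assumed responder rates, an assumed association, a normally distributed covariate and a single visit with 127 per arm. The planned repeated-measures model could give somewhat different gains. To say that the trial is giving up power would go beyond the documents.

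**What to change.** Before unblinding, add the continuous baseline MDS-UPDRS Parts II and III combined score as a fixed effect in SAP 5.10.2.1. In the population-level summary of 5.10.2, add a clause saying that the odds ratio is conditional on baseline severity and MAO-B inhibitor use. Because the protocol's PGIC model does not contain this covariate, record the addition as a change from it.

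The cost is two short SAP edits, one degree of freedom, and a slightly different odds ratio (2.05 to 2.14 where the marginal value is 2.00, for covariate odds ratios of 1.5 to 2.0).

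Two related items need no change. Responder percentages by visit and group are already planned in 5.10.2.1. Section 5.12 sends the CGI-I and PGIC scores to the model of 5.9.2, which read literally already carries the baseline combined score.
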